12.2. General Statistical Methods

12.2.1. Analysis Sets

All subjects actively enrolled in the study (i.e. who meet all eligibility criteria at the time of enrolment into the study and who have given written informed consent) will be included in the primary endpoints analyses.

12.2.2. Number of Subjects per Investigative Site

Approximately 40 investigational sites in Japan will enroll a minimum of 556 to power all primary endpoint for each cohort and a maximum of 900 eligible subjects. If a site does not enroll a subject within a 3-month time period, the site may be replaced at the discretion of the sponsor.

12.2.3. Descriptive Statistical Methods

Descriptive statistical methods will be used to summarize the data from this study, with hypothesis testing performed for the primary endpoints. Unless otherwise stated, all statistical testing will be one-sided and will be performed using a significance (alpha) level of 0.025.

Continuous variables as a minimum will be described by number of non-missing observations (n), arithmetic mean (Mean), SD, minimum (Minimum), median (Median), and maximum (Maximum). One additional decimal point for mean and median and 2 additional decimal points for SD will be used.

Categorical variables will be presented using the number of non-missing observations (n) or the number of subjects in the population (N) as applicable and percentages (%). Percentages will be rounded to one decimal place. Unless otherwise stated, two-sided 95% confidence intervals (CIs) will be provided when relevant. The two-sided 95% CI will be presented as it provides the one-sided 97.5% lower (resp. upper) limit when the upper (resp. lower) bound is ignored to assess superiority.

12.3. Data Analyses

Exploratory analyses for the pooled ICD and CRT-D Cohorts versus Non-Device Cohort (ESC Guideline 2016 Indicated but not implanted) will be performed using propensity score matching method in order to compare the all-cause mortality rate and the composite rate of HF events between the pooled ICD and CRT-D Cohorts versus the Non-Device Cohort regarding 7 risk factors at baseline (age >70 years, smoking today or during last 5 years, prior MI, diabetes type I and II, chronic atrial fibrillation, renal dysfunction, NYHA Class III or IV).

A propensity matching score will be generated for each subject by logistic regression where the 'device' variable (device implantation Yes/No) is the dependent variable and the

covariates are the 7 risk factors in the model. Each subject in the pooled ICD and CRT-D Cohorts will be matched to a subject in the Non-Device Cohort based on the closest propensity score.

Subjects in the pooled ICD and CRT-D Cohorts will then be compared to those in the Non-Device Cohort before propensity score matching and after propensity score matching for each of the 7 risk factors using the Chi-square test. This technique enables evaluation of the success of propensity matching.

Finally, the all-cause mortality rate and the composite rate of HF events (outcomes) will be compared between the pooled ICD and CRT-D Cohorts and the Non-Device Cohort using the Chi-square test.

The detailed statistical method for propensity score matching will be presented in an SAP.

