The present study is intended to evaluate the risk of SCD and heart failure (HF) events in known high risk subject cohorts. Implantation of pacing and defibrillation devices that provide cardiac resynchronization therapy (CRT) is proven to be a highly effective treatment for selected subjects with cardiac arrhythmia and HF. However, the question remains whether study data from the United States (US) and Europe are fully applicable in Japan despite genetic and cultural differences. Implantable cardioverter-defibrillator (ICD) and cardiac resynchronization therapy-defibrillator (CRT-D) devices for many patients with high risk on SCD have not been studied in a prospective study in Japan. Therefore, this registry study intends to collect clinical data in defined ICD and CRT-D treatment cohorts in a study population with a majority of Japanese subjects so that further knowledge is added to improve medical device treatment options.

An optimized ICD treatment was studied in the Automatic Defibrillator Implantation Trial (MADIT) Reduce Inappropriate Therapy (RIT) trial^{3,4} where 1500 subjects from US and Europe have been enrolled in 3 arms. Arm B and Arm C, with a high cut off rate of >200 bpm and with a prolonged delay in therapy at 170 bpm have shown a significant reduction in unnecessary and inappropriate treatment.⁴

The mortality rate in pacemaker cohorts is usually very high and it is the question whether a different device therapy may help selected patient cohorts. The defined cohort in this HINODE study is selecting especially subjects with a heart failure background which have a high incidence of further progression of the disease.⁶ It is the question whether those subjects can be identified during de novo implants or during device replacement so that a different device therapy would have the potential to impact the progression of the disease. The selected cohort has at least 3 risk factors which may lead to an increased incidence of Non-sustained ventricular tachycardia (NSVT) or other ventricular arrhythmia. The use of a risk score in a PM population may help to identify subjects who may benefit from CRT-P or CRT-D.

The outlined risk factor MI in the HINODE study is used for subjects with one or more clinically documented, enzyme-positive myocardial infarctions, or clear evidence of pathologic Q waves or generally accepted imaging techniques.

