9.3.2. Exclusion Criteria for the ICD and CRT-D Cohorts

Subjects who meet any one of the following criteria (Table 9.3-2) will be excluded from the ICD and CRT-D cohorts of the study.

Table 9.3-2: Exclusion Criteria for the ICD and CRT-D Cohorts

1. CRT implanted in subjects with a QRS duration <130 ms
2. Subjects who have recovered from a ventricular arrhythmia causing hemodynamic instability
3. Subjects with NYHA Class IV (for ICD subjects)
4. Existing or previously implanted ICD, CRT-P, CRT-D, or pacemaker device system.

Abbreviations: BSC = Boston Scientific; CRT = cardiac resynchronization therapy, CRT-D = cardiac resynchronization therapy-defibrillator; ICD = implantable cardioverter-defibrillator

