12.1.6. Sample Size

The pre-specified primary endpoints sample sizes are outlined in **Error! Reference source not found.** The minimum required sample sizes to sufficiently power each primary endpoint at 90% and account for up to 20% attrition are lower than the final sample sizes.

The final sample sizes for the device cohorts (ICD: 117 to 270 subjects; CRT-D: 95 to 250 subjects; PM/CRT-P: 172 to 200 subjects) will ensure that there will be a sufficient number

of subjects to evaluate each primary endpoint, as well as provide ample data to characterize the safety, performance and efficacy profiles based on secondary and additional endpoints.

The final sample size for the non-device cohort (Non-device [ESC Guideline 2016 Indicated but not implanted]: 172 to 300 subjects) will ensure that there will be a sufficient number of subjects to compare the rate of sudden cardiac death in the non-device cohort with the rate of appropriately treated ventricular arrhythmias or sudden cardiac death in the defibrillator cohort (ICD, CRT-D).

In case of low enrollment rates, enrollment may be closed after the statistically required calculated minimum sample size was completed.

Table 12.1-1: Endpoint Sample Size Estimates

Endpoint	Measurement	Performance Goal Hypotheses ¹	Expected Performance ²	Power	Number of Subjects	
					Needed for Analysis	Required Minimum Sample size Enrolled for ≤20% Attrition
Primary Endpoint for ICD Treated Subjects	Ventricular arrhythmia ³ associated symptoms free-rate from 0 to 12 months	H_0 : Rate ≤ 85.0% H_A : Rate > 85.0%	95.0%	90%	93	117
Primary Endpoint for CRT-D Treated Subjects	Ventricular arrhythmia ³ associated symptoms free-rate from 0 to 12 months	H_0 : Rate ≤ 87.0% H_A : Rate > 87.0%	97.0%	90%	76	95
Primary Endpoint for PM/CRT-P Treated Subjects	All-cause mortality free-rate (survival rate) from 0 to 12 months	H_0 : Rate ≤ 80.0% H_A : Rate > 80.0%	90.0%	90%	137	172
Primary Endpoint for Non-device Subjects (ESC Guideline 2016 Indicated but not implanted)	All-cause mortality free-rate (survival rate) from 0 to 12 months	H_0 : Rate ≤ 80.0% H_A : Rate > 80.0%	90.0%	90%	137	172

¹ Hypothesis test based on a one-sided alpha level of 0.025; clinically accepted delta of 10%, subtracted from expected performance

² Determined from prior comparable studies

³ Appropriately treated

CRT-D = cardiac resynchronization therapy-defibrillator; ICD = implantable cardioverter-defibrillator;

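### The exploratory device versus Non-device comparison pools ICD with CRT-D and leaves QRS/LBBB out of the score, so its HF result can depend on the device mix; device-specific matched comparisons should be added.

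*Combined protocol and SAP*

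**What the plan says.** Section 12.3 and the synopsis (Statistical Test Method) introduce "Exploratory analyses for the pooled ICD and CRT-D Cohorts versus Non-Device Cohort" by propensity score matching. The stated purpose is this: "compare the all-cause mortality rate and the composite rate of HF events between the pooled ICD and CRT-D Cohorts versus the Non-Device Cohort". In the logistic model, "the 'device' variable (device implantation Yes/No) is the dependent variable". The covariates are seven risk factors, listed as follows: "age >70 years, smoking today or during last 5 years, prior MI, diabetes type I and II, chronic atrial fibrillation, renal dysfunction, NYHA Class III". The last item also takes in Class IV. The eligibility lists contain nine factors; the two dropped are LVEF and QRS/LBBB. After matching, mortality and HF events "will be compared between the pooled ICD and CRT-D Cohorts and the Non-Device Cohort using the Chi-square test".

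No contrast of either device type with Non-device is described. Sections 12.3.3 (subgroup) and 12.3.5 (multivariable) are marked not applicable. By contrast, Sections 12.1.1.2 and 12.1.2.2 analyse the primary arrhythmia endpoint both combined and by device. Section 12.1.5 lists the HF composite for the ICD, CRT-D and PM/CRT-P cohorts, as a descriptive secondary endpoint.

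The physician chooses the device (Section 8). The ratio is bounded only by the cohort ranges in Section 12.1.6: "ICD: 117 to 270 subjects; CRT-D: 95 to 250 subjects".

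**The concern.** The synopsis objectives name ICD treatment and CRT-D treatment as two things on which evidence is wanted. The Introduction says that device implantation providing "cardiac resynchronization therapy (CRT) is proven to be a highly effective treatment for selected subjects with cardiac arrhythmia and HF", and the guideline table in Section 27.5 recommends CRT in wide-QRS patients to reduce morbidity and mortality. An effect on HF events that differs between the two devices is therefore a realistic possibility. A single yes/no exposure averages over it, with weights set by who happened to be enrolled and matched.

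The controls add a second problem. Table 9.2-5 admits Non-device subjects through an ICD-type limb with no QRS floor, or through a QRS limb. Section 9.3.2 excludes "CRT implanted in subjects with a QRS duration <130 ms" from the device cohorts. With QRS and LBBB outside the score, nothing prevents a CRT-D subject from being matched to a control with QRS below 130 ms.

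What is at stake is the reading of a null or modest pooled HF result. It could mean little effect of either device, or an effect of one diluted by the other.

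**Working it through.** **1. The plan's own sizes.** Exact one-sample binomial, one-sided 0.025, power at least 90%, then divided by 0.80 for attrition (Table 12.1-1):

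- ICD, 85% v 95%: n = 93 (power 0.906); 93/0.80 = 116.25, so 117.
- CRT-D, 87% v 97%: n = 76 (power 0.922); 76/0.80 = 95.
- PM/CRT-P and Non-device, 80% v 90%: n = 137 (power 0.910); 137/0.80 = 171.25, so 172 each.
- Sum: 117 + 95 + 172 + 172 = 556.

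All agree with the plan. They size the primary endpoints; the plan gives no size, power or device ratio for this comparison.

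**2. Permitted CRT-D share of enrolled device subjects, s.**

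| ICD:CRT-D | s |
|---|---|
| 270:95 | 95/365 = 26% |
| 117:95 | 95/212 = 45% |
| 270:250 | 250/520 = 48% |
| 117:250 | 250/367 = 68% |

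**3. Dependence on the mix.** With a common control risk, pooled difference = (1 − s) × ICD difference + s × CRT-D difference. It is free of s only if the two differences are equal. This needs no assumed rate.

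**4. Illustration.** Assumptions, none from the documents: Non-device 12-month HF rate 20%, ICD relative risk 1.0, CRT-D relative risk 0.65. The CRT-D difference is 20% × 0.35 = 7.0 points and the ICD difference is 0.

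- 270:95: 7.0 × 0.260 = 1.8 points
- 117:95: 7.0 × 0.448 = 3.1 points
- 117:250: 7.0 × 0.681 = 4.8 points

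The ratio of the extremes is 0.681/0.260 = 2.6, from mix alone.

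**5. Range.**

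- Base rates 10% to 30%, CRT-D relative risks 0.6 to 0.8, no ICD effect: pooled difference from 0.10 × 0.20 × 0.260 = 0.5 points to 0.30 × 0.40 × 0.681 = 8.2 points. The CRT-D difference itself runs from 2 to 12 points.
- CRT-D relative risk 0.6, ICD 1.0: pooled relative risk 1 − 0.4s, which is 0.73 at 117:250 and 0.90 at 270:95.
- CRT-D 0.7, ICD 1.1: pooled relative risk 0.83 at 117:250 and 0.996 at 270:95.

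**6. Enrolled and matched mix.** The corners have 365 and 367 device subjects against at most 300 Non-device. Not all can be matched 1:1 without replacement, so the share in the matched set may differ again from step 2.

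**7. Power at minimum sizes.** Normal approximation, two-sided 5%, base rate 20%, no ICD effect. Assume half of the 172 Non-device subjects, 86, are CRT-indicated.

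| Comparison | CRT-D relative risk | Power |
|---|---|---|
| Pooled, 212 v 172 | 0.60 | 15% |
| CRT-D, 95 v 86 | 0.60 | 31% |
| CRT-D, 76 v 69 (20% attrition) | 0.60 | 26% |
| CRT-D, 95 v 43 (one quarter indicated) | 0.60 | 25% |
| Pooled, 212 v 172 | 0.65 | 12% |
| CRT-D, 95 v 86 | 0.65 | 25% |

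These figures ignore the matching.

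**The case against.** The analysis is labelled exploratory, and Section 12.3 leaves matching detail to an SAP; that detail is not in the text reviewed. This limits the stakes. It does not remove the point, because Section 12.3 already fixes the pooled exposure, the covariates and the test.

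Pooling also answers a coherent question. The Non-device cohort is defined by meeting ICD or CRT-D guidelines without an implant, so implanted v not implanted among indicated patients is a legitimate strategy contrast. That stands, and it is why the pooled result should stay.

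Four stronger readings are tempting and are not supported:

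- *The protocol says an ICD does nothing for HF.* It does not. The Introduction sentence concerns devices that provide CRT, and the guideline table recommends CRT; neither addresses ICD effects on HF events. The zero ICD effect in the illustration is an assumption.
- *The reader could not tell the devices apart at all.* If the secondary HF endpoint is reported by cohort, the ICD and CRT-D rates will be visible. What is missing is a matched contrast of each with Non-device.
- *The mortality comparison is shown to mislead.* The same algebra applies if the effects differ, but the figures here concern HF events only.
- *ICD subjects should be compared only with narrow-QRS controls.* ICD entry has no upper QRS limit and wide QRS is a countable risk factor (Table 9.2-2), so that restriction would itself unbalance QRS. The two limbs of Table 9.2-5 can also overlap.

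Matching to narrow-QRS controls is in part a covariate problem separate from pooling. Adding QRS to the pooled score would help with it, but the treated arm would still hold two treatments.

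**Conclusion.** The concern holds as an inexpensive improvement to an exploratory analysis. Whenever ICD and CRT-D differ in their effect on HF events, the planned estimate depends on a mix that is not fixed by design and is bounded only at 26% to 68% CRT-D among those enrolled. The omission of QRS/LBBB also allows CRT-D subjects to be matched to controls ineligible for the CRT-D cohort. The share range and the dependence on mix follow from the documents and algebra. The 1.8 to 4.8 points against 7.0 rest on assumed rates and relative risks and on a common control risk. No primary endpoint analysis is affected. Splitting by device gives a more interpretable estimate and still not a powered test.

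**What to change.** In Section 12.3, the synopsis and the SAP:

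1. Keep the pooled comparison, and report the ICD:CRT-D mix in the matched set.
2. Add matched comparisons of ICD v Non-device and of CRT-D v Non-device, each with its own propensity score including QRS duration and LBBB.
3. For CRT-D, restrict controls to Non-device subjects who meet the CRT-D cohort's own ECG and rhythm criteria, including the atrial fibrillation limb in the synopsis. That limb takes QRS of at least 130 ms without a morphology requirement, so the QRS limb of Table 9.2-5 is not an adequate substitute.
4. For ICD, balance QRS and LBBB through the score and do not exclude wide-QRS controls.
5. State that HF events will be interpreted mainly by device type.

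The cost is wording only. Intrinsic QRS is required at enrolment and QRS morphology and width are part of the risk factor assessment (Table 11.1-1, Section 11.4); ECGs are read centrally for eligibility (Section 22.3). The downside is smaller groups, wider intervals and the low power shown in the working, so estimates with confidence intervals should carry the interpretation.

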Statistical Test Method (continued)	
 • The primary endpoints above will be performed for ICD and CRT-D cohorts combined (primary analysis) as well as for ICD and CRT-D treated subjects separately (for descriptive purpose). • For PM/CRT-P treated subjects, the all-cause mortality free-rate (survival rate) from implant will be calculated as the proportion of actively enrolled subjects who are alive 12 months after implant. The null hypothesis will be rejected and the endpoint considered met if the lower one-sided 97.5% confidence bound for the proportion of subjects with no death is greater than 80.0%. • For Non-device subjects (ESC Guideline 2016 Indicated but not implanted), the all-cause mortality free-rate (survival rate) from enrolment will be calculated as the proportion of actively enrolled subjects who are alive 12 months after enrolment. The null hypothesis will be rejected and the endpoint considered met if the lower one-sided 97.5% confidence bound for the proportion of subjects with no death is greater than 80.0%. • Exploratory analyses for ICD and CRT-D Cohorts combined versus Non-Device Cohort (ESC Guideline 2016 Indicated but not implanted): propensity score matching comparison of all-cause mortality rate and composite rate of HF events between pooled cohorts with device (ICD and CRT-D) versus the Non-Device Cohort regarding 7 risk factors at baseline (NYHA Class III or IV, renal dysfunction [chronically BUN >26 mg/dL / ≥ 9.28 mmol/L], diabetes type I and II, chronic atrial fibrillation [permanent or persisting according to ESC Guideline 2016], prior MI, age >70 years, smoking today or during last 5 years). 
Further details on analytical methods can be found in Section 12 of the CIP

Sample Size Parameters	
ICD Treated Subjects:
 
The minimum required sample size to statistically power the ventricular arrhythmia associated symptoms free-rate through 12 months post implant is 117 subjects. Sample size was calculated assuming a 95.0% ventricular arrhythmia associated symptoms free-rate, a performance goal of 85.0%, one-sided alpha level of 0.025, 90% power, and 20% attrition.

Heart Failure Indication and Sudden Cardiac Death Prevention Trial Japan
Hinode

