11.3. Informed Consent

During the Enrolment and Consenting Visit (Section 11.4), a qualified center representative will review the consent with a potential subject. The subject will be encouraged to ask any questions about the study. All questions from the subject should be addressed prior to the subject signing the informed consent. If the subject signs the informed consent, a signed copy should be provided to the subject and the original should be filed in the electronic or paper medical records. Documentation of the consent process by the person obtaining consent should be filed in the subject study file. No study-specific data collection of any procedure should be conducted prior to consent.

11.4. Enrolment and Consenting Visit (Day 0, 0 to 45 days post implant procedure, alternative >90 days post MI)

Prior to initiating any study procedures, the investigator must ensure that appropriate informed consent has been signed and dated (Section 21). Subjects will sign and date the ICF post successful implant or minimum 3 months post MI, PCI, or CABG.

Subjects who meet all of the entry criteria and consent to the evaluation are eligible. The enrolment for this registry will occur up to 45 calendar days after the device system implantation.

Subjects are considered enrolled after they have met all inclusion criteria, none of the exclusion criteria, and provided written informed consent in accordance with applicable regulatory agency and EC requirements.

The data collection at enrolment includes: demographic data, clinical assessment, medical history and co-morbidities, subject information and medical history; subject status and clinical assessment per SOC; and details on previously/currently implanted devices.

Subject information and medical history

- **Demographic data:** age at time of consent; gender.
- **Clinical assessment:** weight, height, BMI, blood pressure, NYHA Class.
- **Medical history / co-morbidities:**
 - **Subject etiology:** ischemic cardiomyopathy; idiopathic cardiomyopathy; valvular cardiomyopathy; hypertrophic cardiomyopathy; congenital heart disease; infiltrative disease; neuromuscular disease (including myotonic dystrophy and Kearns-Sayre syndrome).

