 - Device cohorts: data obtained within the last 3 months prior to enrolment are to be provided
 - Non-device cohort: latest data obtained within the last 12 months prior to enrollment in case there was no documented HF decompensation, MI or revascularization, otherwise within the last 3 months prior to enrollment are to be provided
- **MRI scan:** data on actual number of MRI scans performed according to center's SOC since the implant procedure, including information about scanned body parts, will be collected.
- **Physician's judgment:** judgment on therapy status / outcome / CRT therapy delivery (success yes/no) / defibrillator therapy (ATP/Shock delivered: yes/no).
- **Biomarkers for heart failure:** parameters as routinely evaluated prior to device implant or as part of standard visit for non-device subjects will be documented by the

site teams in the eCRF including name of parameter, date of analysis, result, and normal range according to local lab.

Collected standard biomarkers are: amino-terminal pro-peptide B-type natriuretic peptide (NT-proBNP), BNP, Troponin T, Troponin I, creatinine, BUN, and estimated glomerular filtration rate (eGFR)

Optional additional biomarkers collected from SOC diagnostics are: CK-MB, C-reactive protein, TNF-alpha, galectin-3 (Gal-3), parathyroid hormone (pTH), CA125, ST2

However, the identification of laboratory parameters as biomarkers for heart failure is left to the discretion of each individual investigator.

Risk factor assessment

The following risk marker will need to be assessed (at all FU scheduled and unscheduled):

1. Myocardial infarction status
2. Last available EF status (value/ date)
3. Atrial fibrillation
4. Smoking
5. QRS morphology and width
6. Renal function
7. Diabetes type I and II
8. NYHA assessment
9. Age of subject

- Therapy judgment: appropriate, inappropriate, both, unclear
- CRT only: V-V timing of programmed vector
- MRI scan done during last 6 months observational period: yes/no
- Reason for MRI scan documented as related to diagnostics or related to a known SAE
- After any MRI, appropriate pacing and sensing need to be verified and documented as an unscheduled visit. In case of an increased pacing threshold or inappropriate sensing or any other device abnormality, an event report must be completed.

Latitude

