12.3.6. Other Analyses

Descriptive statistics of subject demographics and baseline characteristics will be presented. A list of potential baseline variables is categorized below:

- Demographics: age (numeric and % \leq 70 years/ % $>$ 70 years), gender (%)
- Clinical: NYHA Class, chronic atrial fibrillation (%), paroxysmal atrial fibrillation (%), atrioventricular block (%), QRS morphology, intrinsic or paced QRS width, LVEF (numeric and % normal, fully preserved [\geq 50%]/ % partially preserved [40%-49%]/ % reduced [$<$ 40%]), blood pressure, BMI, heart rate
- Medical history/co-morbidities: single/multiple MI, hypertension, diabetes type I and II, current smoking, renal dysfunction
- Current medications: ACE-inhibitor, Angiotensin II receptor antagonist, antiarrhythmic, anticoagulant, antiplatelet, aldosterone-antagonist, beta-blocker, digitalis, diuretics, statins, calcium antagonists, oral hypoglycemic agent, non-insulin injectable, insulin.

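### The exploratory propensity score and its balance check use the same yes/no cut-points, so age and renal differences inside a category are not matched directly and cannot be seen

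*Combined protocol and SAP*

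**What the plan says.** Section 12.3 fits a logistic model for device implantation (yes or no). It states that the "covariates are the 7 risk factors in the model" and lists them as "age >70 years, smoking today or during last 5 years" and "prior MI, diabetes type I and II, chronic atrial fibrillation, renal dysfunction, NYHA Class III or IV". The synopsis (Statistical Test Method) gives the renal cut-point: "renal dysfunction [chronically BUN >26 mg/dL". LVEF and QRS are not among the seven.

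Each device subject is matched to the Non-device subject with the closest score. No caliper, ratio or rule on reuse of controls is given. The seven factors are then compared by Chi-square before and after matching, and the section says of this step: "This technique enables evaluation of the success of propensity matching". Further detail is left to an SAP. The reviewed documents contain no SAP text on propensity matching.

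Numeric values exist for the variables that matter:
- **Age.** Section 11.4 collects "age at time of consent; gender". Section 12.3.6 plans a numeric summary ("Demographics: age (numeric and" percentages either side of 70).
- **LVEF.** A measured value is a general entry criterion (Table 9.2-1), and Section 12.3.6 lists LVEF as numeric.
- **Renal function.** Section 11.4 names "creatinine, BUN, and estimated glomerular filtration rate (eGFR") among the standard biomarkers, but Table 11.1-1 makes biomarkers standard of care only. The risk factor assessment is required.

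**The concern.** To this score, a subject aged 71 and one aged 88 are the same, as are BUN values of 27 and 49 mg/dL. Any cohort difference of that kind is balanced only indirectly, through its association with the other matched factors. A test on the same cut-points cannot reveal what is left.

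LVEF raises a related issue. The ICD, CRT-D and Non-device criteria all require 35% or less, so a yes/no LVEF factor would be constant. Only the numeric value could adjust for severity within that range, and it is not used.

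The investigator decides who receives a device, and this is the plan's only covariate-adjusted comparison of device with Non-device subjects. If unimplanted subjects are older or have worse renal function, the remaining difference would be read as a device benefit. The documents do not say whether that is the direction.

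**Working it through.** The plan states no figure for this analysis, so there is none to reproduce.

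**Inputs from the documents.** Age cut 70; BUN cut 26 mg/dL; chronic BUN of 50 mg/dL or more excluded (Table 9.3-1). Cohort sizes from Section 8.2: device 117 + 95 = 212 up to 270 + 250 = 520; Non-device 172 to 300.

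**Assumptions.** All distributions, gaps and hazard slopes below.

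**1. Age, one cut, perfect balance on it.** For mean m, SD s and z = (70 − m)/s, let p = 1 − Φ(z). The mean above the cut is U = m + sφ(z)/p, and below it L = m − sφ(z)/(1 − p). With D for device and N for Non-device, the remaining gap is p_D(U_N − U_D) + (1 − p_D)(L_N − L_D).
- Device mean 66, SD 10: z = 0.40, p = 0.345, U = 76.69, L = 60.38.
- Non-device mean 71, SD 10: z = −0.10, U = 78.35, L = 62.37.
- Remaining: 0.345 × 1.66 + 0.655 × 1.99 = 1.88 of 5 years, or 38%.
- Means (66, 71), (64, 70), (66, 76) and (68, 73) with SD 10 or 12 give 36% to 40%.

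**2. Effect on the comparison.** If the mortality hazard rises 3% to 5% per year of age, 1.03^1.88 = 1.06 and 1.05^1.88 = 1.10. For a 10-year gap (66 v 76), 3.6 years remain and the hazard ratio is 1.11 to 1.19.

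**3. BUN.** The same calculation on the log scale, with medians 20 and 24 mg/dL, leaves 42% at log-SD 0.4 and 40% to 46% over log-SD 0.3 to 0.5. With values truncated at 50, medians of 18 to 24 and log-SD 0.3 to 0.4, 32% to 53% remains.

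**4. Position of the cut.** For a small shift in a normal variable cut k SD from its mean, the share left is 1 − φ(k)²/[Φ(k)(1 − Φ(k))]. This is 36% at k = 0 (that is, 1 − 2/π), 42% at 0.5, 56% at 1 and 73% at 1.5. Allowing for larger shifts, the ranges are 52% to 59% at 1 SD and 69% to 75% at 1.5 SD.

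**5. Help from the other factors.** Exact matching on all seven factors, all shifted together by 0.4 SD, leaves the following share of the age and BUN differences:

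| Correlation among factors | Share left |
|---|---|
| 0 | 38–40% |
| 0.2 | 23–25% |
| 0.4 | 17–18% |

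**6. The plan simulated.** Age gap 5 years, SD 11; BUN ratio 1.2; other factors not shifted; each Chi-square at two-sided 0.05.
- *Controls reused, 212 v 172 and 520 v 300, correlation 0 to 0.5:* 34% to 43% of the age gap and 34% to 40% of the BUN gap remain. All seven Chi-square tests pass in 79% to 89% of runs, and the age and BUN tests reject in 0% to 2%. A t-test on numeric age rejects in 34% to 90% of the same runs.
- *No reuse, 212 v 172:* every Non-device subject is used, 99% to 100% of the gap remains, and the check fails in 99% to 100% of runs.
- *Numeric age and log BUN in the score, controls reused:* about 0% to 2% remains.
- *172 device subjects matched without reuse from 300:* 20% to 26% remains with numeric terms, against 37% to 45% with yes/no factors.

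**The case against.** The strongest reply is that the stakes are low and the size is assumed. The analysis is labelled exploratory, has no hypothesis or power, and is not among the secondary endpoints. At the protocol's 10% one-year mortality with 172 subjects per group, the standard error of a log risk ratio is √[2(1/17.2 − 1/172)] = 0.32. A bias of 0.06 to 0.10 on the log scale is then 0.2 to 0.3 standard errors. This stands and is why the point is minor.

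A reader might infer three stronger things that the documents do not support:
- **That at least a third of any age or renal difference survives.** It is not a floor. Step 5 gives 17% to 25% when all the factors move together and are correlated, which is plausible if unimplanted subjects are generally older and sicker.
- **That the check will report success.** That holds when matching is feasible. At the minimum cohort sizes without reuse of controls, the check fails, and Section 12.3 does not say whether controls are reused.
- **That all seven factors are cut numbers.** Prior MI, diabetes, atrial fibrillation and smoking are naturally yes/no. NYHA loses little, since the ICD cohort and the first Non-device entry route admit only classes II and III. LVEF is omitted, not dichotomised.

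Deferral to an SAP is a weaker defence: Section 12.3 already fixes both the covariates and the balance test. Numeric age and LVEF summaries are planned in Section 12.3.6, but not for the matched sets.

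**Conclusion.** The concern holds as a limited point. The score and its check share the same cut-points, so within-category differences in age or BUN are not matched directly and the check cannot detect them. This follows from the text and needs no assumption.

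The size does rest on assumptions. For a simple shift in one variable, roughly a third or more remains (36% to 40% for age under normal distributions). The full range is about 17% to 75%, depending on where the cut falls and how far the other matched factors are correlated with age and BUN. The hazard ratio of 1.06 to 1.10 further assumes a 5-year age gap and a 3% to 5% hazard increase per year. Severity is minor.

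**What to change.** In Section 12.3 and the SAP:
- Enter age as a continuous term, for example a restricted cubic spline.
- Add numeric LVEF. State that the measurement window differs: 3 months before enrolment in the device cohorts, up to 12 months in Non-device subjects without intervening decompensation, MI or revascularisation (Table 9.2-1).
- Use numeric BUN or eGFR where available. Keep the required yes/no renal factor, since it refers to chronic BUN and a single laboratory value does not replace it. State a rule for missing values.
- Keep diabetes, atrial fibrillation, prior MI and smoking as yes/no.
- Judge balance by standardised mean differences on the numeric values as well as on the seven factors.

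No new procedure is needed, and Section 12.3.7 allows an amended SAP before database lock. The costs are some missing renal values, possibly unequal between cohorts, and slightly more analysis work. There is also a trade-off: in the simulation with reused controls and numeric terms, all seven Chi-square tests passed in only 41% to 59% of runs, which is why balance should be shown on both scales. Where controls are scarce the gain is partial (20% to 26% still remains in step 6), so the SAP should also state whether controls are reused.
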